## **8.0 PHYSICIAN AND PATIENT DISPOSITION**

Physician disposition will be summarized overall and by country using descriptive statistics for the following parameters: number of solicited, responding, participating and active physicians, number of non-participating physicians and reason for non-participation, and number of patients included per physician. The number of physicians who returned the Screening logs will also be described.

Patient disposition will be summarized overall and by country using descriptive statistics for the following parameters: number of patients recorded in screening logs, number of patients in the Eligible screening log population and reason for exclusion, number of included patients, number and percentage of patients in the Analysis population and reason for exclusion, number of follow-up visits per patient, dates of the first and last date of the first Ozurdex injection in the study eye, date of the last follow-up visit and study duration (months) [DV] for patients from the Analysis population.

The proportion of patients from the Eligible screening log population actually included in the study will also be calculated using the variable '*Chart entered in EDC (Yes/No)*' from the Screening log. This proportion will enable to assess the representativeness of patients included in the study compared to patients not included.

## **9.0 DESCRIPTION OF THE ELIGIBLE SCREENING LOG POPULATION**

Analysis will be performed overall and:

- by inclusion in the study (Yes vs. No). It is to be noted that due to patient anonymization it will not be possible to link patients listed in the screening log and patients included in the study; the number of patients included according to the screening log ('Chart entered to EDC=Yes') may not match with the number of patients actually included in the study according to eCRF. The variable 'Chart entered to EDC' from the screening log will be used to distinguish both of these groups.
- by reason for non-inclusion in the study (Did not meet selection criteria, Lack of time, Quotas were met, Other)

Characteristics of patients of the Eligible screening log population will be summarized using descriptive statistics for the following variables collected in the screening log: age at first Ozurdex implant injection (years), gender, anti-VEGF injections before the first Ozurdex implant injection (Yes, No), number of Ozurdex implant injections in each eye.

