### **7.3.1.2 Patients**

In order to limit bias in the selection of patients, sites will attempt to consecutively select all patients who meet the selection criteria, regardless of demography or other considerations, based on date of first Ozurdex implant injection. All patients meeting the selection criteria, regardless of their selection for the study, will be identifiable in a screening log collecting minimum non-identifying patient information (see Sections 9.2 and 10.1). Characteristics of selected and non-selected patients will be compared to assess patient selection bias and reason for not being selected will be described (patient did not met selection criteria, lack of time, quotas were met, etc.).

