## 9.2 Patient Identification and Selection Procedures

Medical charts will be screened by the investigative site personnel to identify patients who satisfy all the inclusion and none of the exclusion criteria. Once a site has been initiated, site personnel will be invited to complete a screening log with all patients who received their first Ozurdex implant injection from 1 January 2015 until 1 September 2017. Data collected in the screening log, listed in Section 10.1, will help site personnel identify eligible patients. Screening logs will be anonymized before being entered in the study database.

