### *Non-competitive selection of eligible patients*

Upon screening log completion, the sites will proceed through the patients listed in the screening log and will select all consecutive patients who meet the inclusion criteria (Section 8.2.1) and none of the exclusion criteria (Section 8.2.2), starting with patients who received their first Ozurdex injection the closest to 1 January 2015. Patient selection will not be competitive between countries and will stop when the quotas of eligible patients has been reached in each country, i.e. approximately 70 patients in Germany and 30 patients in Switzerland. Consent from patients will not be requested; as the study is retrospective and anonymized, a waiver of consent will have been requested from the Ethics Committees.

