### *Competitive selection of patients - patients who are naïve to anti-VEGF treatment*

During the patient selection process, special attention will be given to patients that are naïve to anti-VEGF treatment prior to first Ozurdex implant injection [REDACTED]

[REDACTED], and sites will be asked to do their best to select a predetermined number of patients who do not meet this exclusion criteria. Recruitment of patients that are naïve to anti-VEGF treatment will stop when approximately 50 patients have been selected in Germany and Switzerland.

[figure not shown]
Overall, patient selection will stop when 150 patients have been selected for the study. The number of patients included at each site, in particular the number of patients that are naïve to anti-VEGF treatment, will be chosen based on feasibility surveys and consultations with the Sponsor.

---

 1 September 2017 was chosen to get at least 1 year of follow-up data on 1 September 2018 for all selected patients.

[figure not shown]

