### **21.3.7 Variables Derived From Data of the Screening Log**

Time from the first Ozurdex implant injection to the most recent follow-up visit prior to 01 September 2018

The variable will be calculated in days as:

Date of the most recent follow-up visit prior to 01 September 2018 – Date of the first Ozurdex injection. As dates are collected in format MM/YYYY, '01' will be considered for the day in the calculation.

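### The SAP 9.0 selection check compares raw injection counts, although inclusion by start date can give included patients longer follow-up and so more injections at the same reinjection pace

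*SAP*

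**What the plan says.** Protocol 7.3.1.2 gives the purpose, and SAP 7.0 repeats it: "Characteristics of selected and non-selected patients will be compared to assess patient selection bias". SAP 9.0 carries this out in the eligible screening log population, by inclusion status and by reason for non-inclusion. Four characteristics are listed: age at first injection, gender, prior anti-VEGF injections (yes/no) and "number of Ozurdex implant injections in each eye".

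Protocol 9.2 sets the order of inclusion. The log covers "all patients who received their first Ozurdex implant injection from 1 January 2015 until 1 September 2017". For non-competitive selection, sites work through it "starting with patients who received their first Ozurdex injection the closest to 1 January 2015", and selection "will stop when the quotas of eligible patients has been reached in each country", at about 70 patients in Germany and 30 in Switzerland. A footnote explains the end of the window: "1 September 2017 was chosen to get at least 1 year of follow-up data on 1 September 2018 for all selected patients".

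The synopsis lists month and year of first injection and of last visit among the log items. SAP 21.3.7 derives from them the "Time from the first Ozurdex implant injection to the most recent follow-up visit prior to 01 September 2018". SAP 6.1 uses this variable only as an eligibility criterion (at least 365 days), and SAP 9.0 does not list it. SAP 8.0 describes study duration for the Analysis population only.

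**The concern.** Start date decides two things at once: who is included before a quota fills, and how long a patient can be observed before the fixed cut-off. Patients left out because quotas were met are the later starters, with less time in which to be reinjected. The raw count can therefore differ between the groups when their reinjection pace is identical.

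The count is also the only one of the four characteristics that bears on the primary outcome. A reader who sees more injections among included patients could conclude that the study selected more intensively treated patients. The table has no follow-up figure for non-included patients that would warn against this. A real difference in pace could also be hidden or reversed. Protocol 8.2 and SAP 4.0 expect the results to generalise to patients with DME treated with the implant in both countries, and this table is part of the evidence for that.

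**Working it through.** **Inputs from the documents.** First injections run from 1 January 2015 to 1 September 2017, a window of 32 months. The cut-off is 1 September 2018, so possible follow-up runs from 44 months down to 12. Eligibility needs at least 2 injections and 12 months of follow-up. Planning values for the interval (Protocol 14.1) are means of 4.7 to 6.7 months and SDs of 1.5 to 3.0 months.

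**The plan's own figure.** Half-width = 1.96 × SD / √150. For SD 1.5, 2.0, 2.5 and 3.0 this gives 0.24, 0.32, 0.40 and 0.48 months, matching the printed 0.2 to 0.5. The plan gives no figure for the selection check.

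**Assumptions.** The documents do not give the share of eligible patients included, the spread of start dates, loss to follow-up or persistence on treatment. The base case takes uniform start dates, inclusion of the earliest 25%, 50% or 75%, the same interval distribution in both groups, and reinjection continuing to the cut-off.

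**By hand.** With uniform starts over 32 months and an included share f, mean start is 32f/2 for included and (32f + 32)/2 for non-included patients. The difference is 16 months whatever f is. The expected gap is about 16 / mean interval:
- 16 / 4.7 = 3.4
- 16 / 6.0 = 2.7
- 16 / 6.7 = 2.4

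**By simulation** (gamma intervals, eligibility applied, half included, mean follow-up 36.0 v 20.0 months):

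| Mean interval (SD), months | Injections, included v non-included | Gap | Reinjections per patient-year |
|---|---|---|---|
| 4.7 (1.8) | 8.23 v 4.83 | 3.40 | 2.41 v 2.30 |
| 6.0 (2.0) | 6.55 v 3.89 | 2.66 | 1.85 v 1.73 |
| 6.7 (2.3) | 5.93 v 3.55 | 2.38 | 1.64 v 1.53 |

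With 25% or 75% included the gaps stay at 2.4 to 3.4.

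**Relaxing the assumptions** (mean 6.0, SD 2.0, half included):

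| Change | Injections, included v non-included | Gap |
|---|---|---|
| One third of included chosen regardless of date | 6.29 v 4.16 | 2.13 |
| Loss to follow-up 2% per month | 5.90 v 3.87 | 2.03 |
| Loss to follow-up 5% per month | 5.01 v 3.71 | 1.30 |
| Loss to follow-up 10% per month | 4.18 v 3.50 | 0.68 |
| All stop after 4 injections | 4.00 v 3.55 | 0.45 |
| All stop after 3 injections | 3.00 v 2.93 | 0.07 |
| All stop after 2 injections | 2.00 v 2.00 | 0 |

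The loss-to-follow-up rows also let the mean interval vary between patients (SD 1.2 months within the total of 2.0).

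**Can the count mislead on direction?** Combine two base-case rows: included patients at 6.7 months and non-included at 4.7. The counts are 5.93 v 4.83, so the slower group looks more heavily treated. The rates are 1.64 v 2.30 per year, the right order.

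**Is the rate clean?** No. (Injections − 1) / follow-up counts the last, incomplete interval as exposure. At an identical 6.0-month interval it gives 1.85 v 1.73 per year, that is 12/1.85 = 6.5 v 12/1.73 = 6.9 months per reinjection. With 25% included it is 1.87 v 1.78 (6.4 v 6.7 months), and with 75% it is 1.83 v 1.67 (6.6 v 7.2 months). The false gap is therefore about 0.3 to 0.6 months. If all stop after 3 injections but stay under observation, the rate is 0.67 v 1.16 per year, a false difference in the opposite direction.

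**The case against.** The table is descriptive, with no test or decision rule, and the study has no hypothesis. Age, gender and prior anti-VEGF use are not affected by follow-up length. The planned breakdown by reason for non-inclusion would concentrate any artefact in the quota-met category, since patients left out for lack of time need not be late starters. Date order is explicit only for the roughly 100 non-competitive patients; for the up to 50 anti-VEGF-naïve patients it is stated only in general terms. Quotas may not bind at every site. All of this stands and limits the size. It does not remove the mechanism: the breakdown by reason would locate the difference but could not separate follow-up from pace.

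A reader might infer that this comparison is the plan's only safeguard against patient-selection bias. It is not. Consecutive selection (Protocol 7.3.1.2), the proportion of eligible patients included (SAP 8.0) and the described reasons for non-inclusion also serve that purpose. It is the only comparison of characteristics between selected and non-selected patients.

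A reader might also infer that the count should give way to a rate. The working does not support that: the rate keeps a residual gap comparable with the study's worst-case precision of 0.5 months, and does worse than the count if patients stop early but stay in follow-up.

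**Conclusion.** The concern holds as a weakness of an ancillary descriptive check. Included patients can show more injections than non-included patients through longer follow-up alone, and nothing planned in SAP 9.0 would reveal this. The gap is about 2.4 to 3.4 injections under uniform start dates and continued reinjection at 4.7 to 6.7 months. It is about 2.1 with a third of inclusion independent of date, 0.7 to 2.0 with 10% to 2% monthly loss to follow-up, and near 0 if most patients stop after two or three injections. The documents do not say which case applies, so it would go too far to say that the check will show a large false difference. Nor does the point imply bias in the primary estimate, which does not use this table.

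**What to change.** In SAP 9.0:

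1. Add year of first injection and the SAP 21.3.7 follow-up time to the table, by inclusion status and by reason for non-inclusion.
2. Report the raw count within bands of year of first injection or of follow-up time.
3. Show reinjections per patient-year beside the count, not in place of it, with a note that both depend on follow-up and on stopping treatment.

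This is a cheap improvement: it needs no new data, only a few table rows and one derived variable. Its limits should be stated:
- Log dates are to the month, so follow-up and rate are approximate.
- The listed log items give injections per eye but one first-injection date, so count and follow-up may refer to different eyes in bilateral patients. Part of Protocol 10.1 is blacked out, so the sponsor should confirm what the log holds.
- Where date order was followed strictly, some bands may hold few patients from one group. Overlap would then come mainly from sites that filled at different times, the anti-VEGF-naïve patients and those left out for other reasons.
- The rate is still affected by follow-up length (about 1.85 v 1.73 per year at an identical 6.0-month interval) and by stopping treatment.

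A count restricted to the first 12 months would remove the artefact (2.55 v 2.56 injections in the 6.0-month simulation), but it needs individual injection dates, which are not among the listed log items.

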## **10.0 DEMOGRAPHICS AND OTHER BASELINE CHARACTERISTICS**

This section describes analyses that will be conducted on parameters that are collected at baseline only. Analyses of parameters that are collected at both baseline and during the follow-up (such as DME status or clinical examination in the study eye) have been considered in other sections (See sections 11.0, 12.0 and 13.0).

Demographics and other baseline characteristics will be summarized using descriptive statistics.

### **10.1 DEMOGRAPHICS**

Demographic characteristics collected include gender, age at baseline (years) [DV], and study eye (OS, OD).

### **10.2 OPHTHALMIC HISTORY AND CURRENT OPHTHALMIC CONDITIONS**

Ophthalmic conditions at baseline will be described by the following parameters:

- History of steroid response (Yes, No) and, if yes, specification of the eye (Study eye, Contralateral eye, Both eyes) [DV].
- Glaucoma (Yes, No) and, if yes: type (Controlled, Uncontrolled), primary or secondary glaucoma, specification of the eye (Study eye, Contralateral eye, Both eyes) [DV], time from onset of glaucoma to baseline (months) [DV], glaucoma treated with medication (Yes, No).
- Ocular hypertension (Yes, No) and, if yes: specification of the eye (Study eye, Contralateral eye, Both eyes) [DV], time from onset of ocular hypertension to baseline (months) [DV], ocular hypertension treated with medication (Yes, No).

### **10.3 MEDICAL HISTORY (OTHER THAN OPHTHALMIC)**

Any relevant chronic medical condition and/or medical conditions in the study eye ongoing at baseline (Yes, No) will be summarized and medical history conditions and events will be described by SOC and PT (MedDRA version 21.1). If several conditions with the same SOC have been reported for the same patient, s/he will be counted once for that SOC. The same rule will apply for conditions presented per PT.

## **11.0 DIABETES AND DME STATUS**

### **11.1 DIABETES AND HbA1c**

Characteristics of diabetes summarized at baseline will include time from diabetes diagnosis to baseline (years) [DV] and type (type 1, type 2). HbA1c measured within 3 months before baseline will be described as a continuous parameter (in %) and as a categorical parameter ( $\leq 8\%$ ,  $> 8\%$ ). The same parameters will be summarized for HbA1c at the last study visit.

### **11.2 DME STATUS**

DME status at baseline and during the follow-up period will be analyzed using information collected in eCRF sections '*Demographics and DME History*' section of the eCRF (DM/F2 form) and '*DME Status*' (DMEF/F17 form).

DME status in the study eye at baseline will be summarized using the following parameters: time from DME diagnosis to baseline (months) [DV], time from onset of DME symptoms to baseline (months) [DV], severity of diabetic retinopathy (no apparent retinopathy, mild non-proliferative diabetic retinopathy, moderate non-proliferative diabetic retinopathy, severe non-proliferative diabetic retinopathy, proliferative diabetic retinopathy), macular ischemia (Yes, No) and peripheral ischemia (Yes, No).

During the follow-up period, severity of diabetic retinopathy in the study eye will be summarized for each Ozurdex reinjection.

## **12.0 CLINICAL EXAMINATION IN THE STUDY EYE**

Lens status, biomicroscopic and ophthalmoscopic examinations, and IOP in the study eye at baseline and during follow-up period will be summarized using descriptive statistics.

### **12.1 LENS STATUS**

At baseline, lens status in the study eye will be first summarized by the number and percentage of patients in each category (Phakic, Pseudophakic, Aphakic). For pseudophakic patients, YAG capsulotomy (Yes, No) and anterior chamber lens (Yes, No) will be described. For phakic patients, nuclear opacity (Present, Absent), cortical opacity (Present, Absent), and posterior subcapsular opacity (Present, Absent) will be described. For each of the three parameters collected for phakic patients, grade (1, 2, 3) will be described.

The number and percentage of patients with a change in lens status from phakic to pseudophakic during follow-up will be summarized [DV]. Among patients with a change from phakic to pseudophakic during follow-up, opacities (nuclear opacity, cortical opacity, and posterior subcapsular opacity) and grade at baseline will be described. If a very small number of patients have a change in lens status, then the variable 'Type of change' will not be derived and the type of change will be described by a listing including raw data from eCRF section '*Biomicroscopy – Lens – Study eye*' (BIL/F8 form) at baseline and at follow-up visits a change has been reported.

A subgroup of patients will be identified by lens status during the study period: phakic throughout vs. pseudophakic throughout vs. change from phakic to pseudophakic [DV].

### **12.2 BIOMICROSCOPY**

At baseline, the number and percentage of patients with biomicroscopy data available for the study eye will be described. Then, for patients with data available, the following parameters will be described:

- Any adverse findings (Yes, No)
- Conjunctiva (bulbar or palpebral): hyperemia (Normal, Trace +0.5, Mild +1, Moderate +2, Severe +3), edema (Normal, Trace +0.5, Mild +1, Moderate +2, Severe +3), subconjunctival hemorrhage (Normal, Trace +0.5, Mild +1, Moderate +2, Severe +3). Adverse findings will also be described as 'Absent vs. Present' [DV].
- Cornea: edema (Normal, Trace +0.5, Mild +1, Moderate +2, Severe +3), superficial punctate keratopathy (Normal, Trace +0.5, Mild +1, Moderate +2, Severe +3). Adverse findings will also be described as 'Absent vs. Present' [DV].

- Anterior chamber: cells (Normal, +0.5, +1, +2, +3, +4), flare (Normal, Faint +1, Moderate +2, Marked +3, Intense +4), hypopyon (Present, Absent) and, if present, level in mm. Findings on cells and flare will also be described as 'Absent vs. Present' [DV].
- Iris/Pupil: pathology (Present, Absent), peripheral iridotomy noted (Yes, No), rubeosis iridis (according to categories 'Normal, +0.5, +1, +2, +3'). Adverse findings will also be described as 'Absent vs. Present' [DV]. Pathologies will be described by PT (MedDRA version 21.1). If more than one pathology with the same PT have been reported for the same patient, s/he will be counted once for that PT.

During the follow-up period, the number and percentage of patients having at least one adverse finding in the study eye (Yes, No) [DV] will be described. Then, for all patients with at least one adverse finding, the type of adverse finding will be described as 'Present, absent' for each pre-listed category: conjunctiva (hyperemia, Edema, subconjunctival hemorrhage), cornea (edema, superficial punctate keratopathy), anterior chamber (cells, flare, hypopyon) and iris/pupil (pathology, peripheral iridotomy, rubeosis iridis). If an adverse finding has been reported more than once for the same category for the same patient, s/he will be counted once for that category. For patients with at least one adverse finding during the follow-up period, a listing will also be presented with all biomicroscopy results at baseline and during the follow-up period.

### 12.3 OPHTHALMOSCOPIC EXAMINATION

At baseline, the number and percentage of patients with ophthalmoscopic data available for the study eye will be described. Then, for patients with data available, the following parameters will be summarized using descriptive statistics:

- Any adverse findings (Yes, No)
- Macula pathology: edema (Present, Absent), hemorrhage (Present, Absent), exudate (Present, Absent), macular scarring (Present, Absent), drusen (Present, Absent), Choroidal neovascularization (CNV) (Present, Absent), cup to disc ratio.
- Vitreous: cells (Normal, +0.5, +1, +2, +3, +4), haze (Normal, +0.5, +1, +2, +3, +4), hemorrhage (Normal, +0.5, +1, +2, +3, +4), posterior detachment (Present, Absent). Findings on cells, haze and hemorrhage will also be described as 'Absent vs. Present' [DV].
- Peripheral retina: hemorrhage (Present, Absent), tear/holes (Present, Absent), laser treatment (Yes, No)

- Other macula pathology and peripheral retina findings will be described by PT (MedDRA version 21.1). If several pathologies/findings with the same PT are reported for the same patient, s/he will be counted once for that PT.

During the follow-up period, the number and percentage of patients having at least one adverse finding in the study eye (Yes, No) [DV] will be described. Then, for all patients with at least one adverse finding, the type of adverse finding will be described as 'Present, absent' for each pre-listed category (macula pathology (edema, hemorrhage, exudate, etc), vitreous (cells, haze, etc), peripheral retina (hemorrhage, tear/holes, etc)) as well as for adverse findings reported as other macula pathology and peripheral retina. If an adverse finding has been identified more than once for the same category for the same patient, s/he will be counted once for that category. For patients with at least one adverse finding during the follow-up period, a listing will also be presented with results of ophthalmoscopic examination at baseline and during the follow-up period.

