## 5 INTRODUCTION

### 5.1 Background

Ozurdex® is a biodegradable solid polymer drug delivery system containing 0.7 mg of dexamethasone. A single-use applicator with a 22-gauge needle that leaves a sutureless self-sealing wound is used to place the dexamethasone implant into the vitreous cavity. The sustained-release formulation was designed to release dexamethasone from the implant for up to 6 months. Ozurdex was granted a marketing authorization in the European Union in 2010 for the treatment of adult patients with macular edema following vein occlusion. In 2011, Ozurdex was furthermore approved for treatment of adult patients with inflammation of the posterior segment of the eye presenting as non-infectious uveitis. More recently, in 2014, Ozurdex was approved for treatment of adult patients with visual impairment due to diabetic macular edema (DME) who are pseudophakic or who are considered insufficiently responsive to, or unsuitable for non-corticosteroid therapy.

DME is a common manifestation of diabetic retinopathy; diabetic retinopathy being microvascular abnormalities seen in the fundus of persons with diabetes. In most studies, DME is defined by hard exudates in the presence of microaneurysms and blot hemorrhages, resulting in increased central retinal thickness (CRT) within one disc diameter of the foveal center. Clinically significant macular edema is the most severe spectrum of DME, and was defined by the presence of edema within 500 µm of the foveal center, or focal photocoagulation scars present in the macular area. The prevalence of DME in population-based studies among type-1 diabetes patients varied between 4.2% and 7.9%. In patients with type-2 diabetes it was between 1.4% and 12.8%. DME is a leading cause of serious central visual loss impairment in diabetic patients. Due to worldwide rise of diabetes mellitus and of life expectancy of those with diabetes mellitus, burden of illness of microvascular complications, such as DME, is expected to increase over time.

Clinical evaluation of DME may be difficult and subjective. Gold standard for DME diagnostic still remains the fluorescein angiography, but optical coherence tomography (OCT) can be used for screening, classification, monitoring, and treatment evaluation of the DME. It has the ability to provide information on CRT as well as distinct morphological features of the edema.

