### Sites and study population

Site selection will aim to recruit qualified ophthalmologists experienced in intravitreal injections who are most likely to treat patients with DME with Ozurdex. A sample of ophthalmologists working in experienced medical retinal centers treating DME patients will thereby be selected.

From a public health and market access perspective, the present study population constitutes a broader real-world patient population than that reflected in clinical trials. The present study design cannot make any conclusions on causal relationships, but can rather explore real-world Ozurdex drug utilization patterns, effectiveness and safety. It is expected that the results from this study may be generalizable to the overall population presenting with DME and treated with Ozurdex in Germany and Switzerland.

Patients may contribute at most one eye into the study. If both eyes meet the inclusion and exclusion criteria, the eye that received the most Ozurdex injections will be chosen as the study eye.

Inclusion criteria are:

1. Patient received at least two Ozurdex implants in the study eye to treat visual impairment due to DME

2. Male or female patient aged  $\geq 18$  years at time of first Ozurdex implant injection in the study eye
3. First Ozurdex implant injection in the study eye occurred after 1 January 2015
4. Patient was followed-up at the site for at least 12 months after the first Ozurdex implant injection in the study eye

Exclusion criterion is:

1. Patient received Ozurdex implants in the study eye as part or during a clinical study

[REDACTED]

[REDACTED]

[REDACTED]

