**At least one adverse finding in study eye at biomicroscopy (Yes, No)**

Using information from eCRF section '*Biomicroscopy in study eye*' (BIO/F9 form) the variable will be derived to:

- Yes, if the variable '*I.1.2. - Any adverse finding?*' is equal to 'Yes' at baseline or at least once at a follow-up visit
- No, if the variable '*I.1.2. - Any adverse finding?*' is equal to 'No' at baseline or at all follow-up visits of the patient
- Missing, if the variable '*I.1.2. - Any adverse finding?*' is missing at baseline or at least once at a follow-up visit and is not equal to 'Yes' at the other follow-up visits.

Biomicroscopy in the study eye: adverse finding categorized as 'Present' vs. 'Absent'

For hyperemia, edema (in conjunctiva and cornea), subconjunctival hemorrhage, superficial punctate keratopathy, adverse finding will be considered:

- Absent, if the result is 'Normal'
- Present, if the result is 'Trace +0.5', 'Mild +1', 'Moderate +2' or 'Severe +3'

For cells, adverse finding will be considered:

- Absent, if the result is 'Normal'
- Present, if the result is '+0.5', '+1', '+2', '+3' or '+4'

For flare, adverse finding will be considered:

- Absent, if the result is 'Normal'
- Present, if the result is 'Faint +1', 'Moderate +2', 'Marked +3' or 'Intense +4'

For rubeosis iridis, adverse finding will be considered:

- Absent, if the result is 'Normal'
- Present, if the result is '+0.5', '+1', '+2' or '+3'

At least one adverse finding in study eye at ophthalmoscopic examination (Yes, No)

The variable will be derived in the same way that the variable 'At least one adverse finding in study eye at biomicroscopy during the follow-up period' (See definition above) using information from eCRF section '*Ophthalmoscopic examination in the study eye*' (OE/F10 form).

Ophthalmoscopic examination in the study eye: adverse finding categorized as 'Present' vs. 'Absent'

For cells, haze and hemorrhage in vitreous, adverse finding will be considered:

- Absent, if the result is 'Normal'
- Present, if the result is '+0.5', '+1', '+2', '+3' or '+4'

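### The follow-up ophthalmoscopy percentage has no new-or-worsened rule and its listed findings include signs of DME, so it should not be read alone as a rate of adverse findings on Ozurdex

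*SAP*

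**What the plan says.** For the follow-up period, SAP 12.3 states that "the number and percentage of patients having at least one adverse finding in the study eye (Yes, No) [DV] will be described". Among patients with a Yes, the type of finding is then shown as present or absent for "each pre-listed category (macula pathology (edema, hemorrhage, exudate, etc), vitreous (cells, haze, etc), peripheral retina (hemorrhage, tear/holes, etc", along with other macular and peripheral retinal findings by preferred term. The same overall item and the individual signs are tabulated at baseline, and flagged patients are listed with their baseline and follow-up results.

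The rule for the flag is in SAP 21.3.6. For biomicroscopy, the variable is Yes if the any-adverse-finding item "is equal to 'Yes' at baseline or at least once at a follow-up visit". The ophthalmoscopy flag follows by cross-reference: "The variable will be derived in the same way that the variable 'At least one adverse finding in study eye at biomicroscopy", applied to the ophthalmoscopy form. Neither section says when a sign of DME should be ticked as adverse, or limits the flag to new or worsened findings.

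Protocol 5.1 describes the disease in overlapping terms: in most studies, "DME is defined by hard exudates in the presence of microaneurysms and blot hemorrhages". Every study eye was treated repeatedly for that disease. Inclusion criterion 1 reads "Patient received at least two Ozurdex implants in the study eye to treat visual impairment due to DME".

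**The concern.** A percentage of patients with an adverse finding during treatment reads like a safety result. Here the listed types of adverse finding begin with edema, hemorrhage and exudate in the macula. A Yes may therefore mean that the DME was still present or had returned, with no injury from the implant or the injection. One Yes visit is enough, and all study eyes were reinjected for DME, so a disease-driven Yes is plausible in many patients.

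Two features make the number harder to read. No criterion for a Yes is given, so sites may differ in whether they tick known, treated DME as adverse, and SAP 7.0 says no queries will be issued. The type rows are described only for flagged patients, so their percentages depend on the same undefined tick. No planned table counts patients whose findings are new or worse than at baseline. A reader would have to extract that from the listing.

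**Working it through.** The documents state no expected value for this flag, so there is no figure to reproduce. The check shows how far the percentage could move with no harm at all, and how visible real harm would be.

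**1. Flag rate without harm.** Let p be the chance that a DME sign leads to a Yes at one follow-up ophthalmoscopy, and k the number of such examinations. Both are assumptions, and visits are treated as independent. Then P(at least one Yes) = 1 − (1 − p)^k.

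| p | k = 2 | k = 4 | k = 8 |
|---|---|---|---|
| 0.05 | 9.8% | 18.5% | 33.7% |
| 0.10 | 19.0% | 34.4% | 57.0% |
| 0.20 | 36.0% | 59.0% | 83.2% |
| 0.50 | 75.0% | 93.8% | 99.6% |
| 0.70 | 91.0% | 99.2% | >99.9% |

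For example, 1 − 0.95^4 = 0.185 and 1 − 0.3^4 = 0.992. Positive correlation between visits of the same patient would lower these values for the same p and k.

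**2. Effect of missing visits.** Under SAP 21.3.6 a Yes stands even if other visits are missing, whereas a patient with no Yes and a missing visit becomes Missing. SAP 21.1 leaves missing values out of the denominator unless otherwise specified. Take p = 0.2, k = 4, and assume 20% of visits missing at random. Using follow-up visits only:
- Yes: 1 − (1 − 0.8 × 0.2)^4 = 1 − 0.84^4 = 0.502
- No: (0.8 × 0.8)^4 = 0.168
- Reported rate: 0.502 / (0.502 + 0.168) = 75%, against 59% with complete data

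**3. Visibility of harm.** With disease background b and an independent rate h of other findings, the flag rate is 1 − (1 − b)(1 − h), so harm adds (1 − b)h. The value 3.5% is the vitreous hemorrhage rate that protocol 5.1 gives for the phase III trials. The value 10% is illustrative.

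| b | rise at h = 3.5% | rise at h = 10% |
|---|---|---|
| 20% | 2.8 points | 8.0 points |
| 50% | 1.75 points | 5.0 points |
| 90% | 0.35 points | 1.0 point |
| 95% | 0.18 points | 0.5 points |

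A count limited to new or worsened findings would show h = 3.5% in 150 patients as about 5 patients (Clopper-Pearson 95% CI 1.1% to 7.6%) and h = 10% as 15 patients (5.7% to 16.0%).

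**4. Type rows.** Suppose 5 of 150 patients have a given finding. If 28 patients are flagged (18.5% of 150), a row based on flagged patients reads 5/28 = 18%. If 149 are flagged (99.2% of 150), it reads 5/149 = 3.4%. The event count is the same in both cases.

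**5. Baseline wording.** Read literally, the Yes rule lets a baseline Yes set a variable that 12.3 presents as a follow-up summary. The No rule has the same form (No at baseline, or No at all follow-up visits). A patient with No at baseline and Yes later would then satisfy both rules. The text may be meant as two parallel definitions, one for baseline and one for follow-up, but it does not say so.

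**The case against.** A reader might infer that the flag counts edema, exudate and hemorrhage directly, that nearly every reinjected eye must score Yes, and that the analysis cannot show harm. The documents do not support any of these.

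- **Mechanism.** The flag comes from one ticked item. The sign fields only describe type among patients already flagged.
- **Size.** Two implants do not imply a Yes at a follow-up ophthalmoscopy. Protocol 5.1 notes that OCT can be used for monitoring and treatment evaluation. The table in the working runs from about 10% to almost 100%, and nothing in the plan says where the study falls.
- **Harm.** Section 12 is a descriptive examination summary. SAP 16.0 assigns safety to the AESI analysis, which draws on a separate form (SAP 15.2.4), carries a 95% CI, and covers hemorrhage, retinal tear or detachment, inflammation and vitreous detachment. SAP 12.3 plans no interval or comparison for the flag. It also gives baseline values, separate type rows and a listing, so edema can be told apart from a tear.
- **Hemorrhage.** It cannot be set aside as a disease sign, because protocol 10.9.2 lists macular and retinal hemorrhage among the AESIs.

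All of this stands, and it limits the point to a minor one. It does not supply a criterion for a Yes, a comparison with the patient's own baseline, or a denominator for the type rows that is free of the flag.

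**Conclusion.** The point holds in a limited form. The follow-up percentage rests on an undefined tick, has no new-or-worsened rule, and sits over finding types that include signs of DME. If sites tick those signs as adverse, it mixes disease activity with any harm and should not be quoted alone as a rate of adverse findings on Ozurdex. How high it would run is unknown: at four visits the range is about 19% to 99% for assumed per-visit rates of 0.05 to 0.7, with independent visits and no harm. Masking of harm is serious only if the disease background is high. A 10% harm rate adds 0.5 points at a 95% background but 8 points at 20%. Because safety is formally assessed through AESIs, this is a minor issue of descriptive reporting.

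**What to change.** In SAP 12.3 and 21.3.6:

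- Keep the existing item, and add a count of patients with at least one item-level finding that is absent at baseline and present at follow-up, or of higher grade than at baseline where the item is graded.
- Treat items as absent at visits where the any-adverse-finding item is No. Give patients with no baseline ophthalmoscopy their own row, since they cannot be classed as new or worsened.
- Show macular edema and exudate separately, as disease status.
- Keep macular and retinal hemorrhage in the new-or-worsened count, with their own row, because they are AESIs. Keep drusen and the other findings coded by preferred term as well. State how cup-to-disc ratio and laser treatment, which are also listed in 12.3, are handled.
- Use all patients with a follow-up ophthalmoscopy as the denominator for the flag and for each type row.
- Reconcile the baseline-or-follow-up wording in 21.3.6 with the follow-up-only summary in 12.3.

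The cost is SAP wording, a few more table rows and slightly more programming. No new data collection is proposed. The SAP does not show that item-level fields are filled in at visits with a No, which is why the treat-as-absent rule is needed.
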